**Table 6 Summary of Key Issues, Their Impact and Strategy to Mitigate Risk**

Potential risk	Summary of data	Impact- eligibility criteria	Strategy-monitoring/stopping criteria
Hypersensitivity	
There may be potential for hypersensitivity reactions from the procedures used in the study or if subjects are allergic to ingredients in the study medications.
 
There is no previous experience of GSK2646264 or of the matched placebo in humans
	
Subjects will be asked at screening if they are allergic to any of the ingredients – if known,
 
Subjects will be excluded from the study if they are allergic to any ingredient of the study medications or if they have previously experienced an anaphylactic reaction.
	
Subjects will undergo regular medical assessment and instructed what action to take in the event of experiencing an allergic reaction.

Skin prick	
There have been rare reports of systemic allergic reactions following skin prick testing (Heinzerling, 2013)
	
Subjects will be excluded from the study if have previously experienced an anaphylactic reaction.
 
Subjects will be excluded from the study if the subject has a reaction which contraindicates to the study
	
Skin prick testing will be performed in a facility with appropriate emergency equipment available in case of the need for treatment for systemic allergic reaction.

Pregnancy and lactation	
There is no data available on the effect of GSK 2646264 in pregnancy and lactation in humans.
 
Fetal malformations were seen after IV dosing to pregnant rabbits with a NOAEL that is expected to exceed the highest expected human exposure by >4 fold. No similar changes were seen in the rat after substantially higher exposure
	
Female subjects of non child bearing potential will be included in Part A of the study.
 
Female subjects that are of child-bearing potential will be required to follow the contraceptive requirements that are outlined in the protocol Section 4.2.1 inclusion criteria for Part B and C.
 
A decision to allow females of child-bearing potential in Parts B and C will be made based on the safety margin from the dosing in Part A of the study.
	
Female subjects that are of child-bearing potential will undergo regular pregnancy testing and treatment stopped immediately if a subject is found to be pregnant during the study.
 
In part B, these subjects must be on oral contraceptives 28 days before screening begins. They will undergo serum pregnancy testing at day -28, day -7 to -4, a serum or urine pregnancy test the day of the start of the study prior to dosing, then testing on an approximately weekly basis and a serum pregnancy test at the follow up visit.
 
In Part C, a serum pregnancy test will be

Potential risk	Summary of data	Impact- eligibility criteria	Strategy-monitoring/stopping criteria
		Nursing females will be excluded from participating in the study.	performed on the day of screening. If this is between Days -13 and -7, a further pregnancy test will not be required until Day 1. However, if the day of screening is between Day -28 and -14, an additional serum pregnancy test will be required between Days -7 and -4. A urine pregnancy test will be required prior to dosing on Day 1
Immune cell effects, including neutropenia	
SYK is involved in immunoreceptor signalling in a number of cell types, including mast cells, basophils, B cells, neutrophils and macrophages (Riccaboni, 2010)
 
Studies with R788 in rheumatoid arthritis identified an increased risk of neutropenia in subjects treated with the oral SYK inhibitor compared to placebo (placebo 0.7%, R788 150mg OD 6.6%, R788 100mg BD 5.9%) (Weinblatt, 2010)
	Subjects with co-morbid conditions that would put them at risk or laboratory values outside the reference range at screening would be excluded from participating in the study.	
The product is being investigated in a topical formulation, which should limit potential systemic exposure. Increasing exposure will be performed gradually.
 
Subjects will undergo regular haematological assessments, including white blood cell counts during the study.
 
Treatment would be stopped if laboratory test results are identified that would put the safety of the subject at risk.

Thyroid	Minimal thyroid follicular epithelial hypertrophy was observed in all doses following iv administration of GSK2646264 in rats for 4 weeks. Thyroid function test (TSH, free and total T3 and T4) at single timepoints 12 hours post last dose were within normal range.	Requirement for normal TSH in all subjects in Part A, and normal TSH, free T4, T4 and T3 in Parts B and C.. Exclusion of subjects with history of Graves' disease or any thyroid cancer	The risk of thyroid effect in this study is considered not to be significant. Monitoring will be based on signs and symptoms and serum markers of thyroid function will be measured in patients in Parts B and C.

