### **3.2.2.3. Additional preliminary data from Part B**

A population pharmacokinetic model integrating all plasma data from part A and the preliminary data from n=4 in part B lead to an estimation of the half life of 57 hours for GSK2646264. This model shows that in order to maintain a 1.8 fold margin with the  $AUC$  NOAEL to allow women of child bearing potential in the trial the doses of 180mg (10% BSA) should be administered every three days, over a total 7 day duration, rather than every day.

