## **5.7. Stopping Criteria for a subject**

### **5.7.1. Liver Chemistry Stopping Criteria**

Liver chemistry threshold stopping criteria have been designed to assure subject safety and to evaluate liver event aetiology (in alignment with the FDA premarketing clinical liver safety guidance).

Study treatment will be stopped **for a subject** if the following liver chemistry stopping criteria is met:

- ALT  $\geq$  3xULN

NOTE: Refer to [Appendix 1](#) for details of the required assessments if a subject meets the above criteria.

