Urine for metabolite analysis			X 			X 						10. Pre dose and pool samples taken 0-12 and 12-24 hours post dose 22. Pool samples taken 0-12 and 12-24 hours post
HIV, Hep B and Hep C screen	X											
Clinical Laboratory Tests	X 	X 		X 		X 	X 		X 	X 		9. Pre-dose AST, ALT, Alkaline Phosphatase, Total Bilirubin Only- : results to be communicated to the GSK Medical monitor on the same day 17.Clinical lab test as per Section 6.3.4 of the protocol

Day:	Screening	-1	1	2	3	4	5	6	7	8	Follow-up	Notes
Visit Window (relative to Day 1)	-28 to -7										Day 9 – Day 11	
Allergen Challenge- Skin Prick Test	X 		X 		X 	X 		X 				3. SPT- Skin Prick Test measurements will be performed ~15-20 mins post challenge. 4. SPT with all 4 specified allergens 5. SPT will be performed 6 hours post dose 7. SPT will be performed 48 hours post dose of Day 4 (on the morning of Day 6)
TSH 	X											2. TSH test only at screening only
Randomisation		X										
Tolerability Assessment			X  ←-----→ only on dosing days 1 to 4									11. Tolerability assessment at pre – and ~6 hours post-dose on dosing days
AE assessment		X	←-----→							X		
Concomitant Medication		X	←-----→							X		
Pharmacokinetic Blood Sample			X 	X 	X 	X 	X 	X 	X 	X 		6. PK blood sample taken at pre dose, 1, 2, 4, 8, 12 and 24hours post previous dose 18. PK blood sample taken at 30, 36, 48 hours, post dose of Day 4 19. PK blood sample taken at 54, 60, 72 hours, post dose of Day 4 20. PK blood sample taken at 78, 84 hours post dose of Day 4 21. PK blood sample taken at 96 hours post dose of Day 4

Day:	Screening	-1	1	2	3	4	5	6	7	8	Follow-up	Notes
Visit Window (relative to Day 1)	-28 to -7										Day 9 – Day 11	
Blood Sample for CD69 expression			X 			X 	X 		X 	X 		12. Predose 13. 4 hours post dose of Day 4 14. 24 hours post dose of Day 4 (sample taken in the morning of day 5) 15. 72 hours post dose of Day 4 16. 96 hours post dose of Day 4
Study Treatment Dosing 			X	X	X	X						8. This will be once daily dosing using fresh bottles at 1% strength in the morning
Discharge from unit											X	
Outpatient visit	X										X	

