### 6.1.3. Part B: Cold urticaria Subjects Time and Event table

Day:	Screening	-1	1	2	3	4	Day 6 to 15	Follow-up (Day 17-19)	Notes
Visit Window (relative to Day 1)	-28 to -7 days 								1. Screening can occur on any day between 28 days and 7 days prior to Day 1 dosing.
Admission to Unit		X							
Informed Consent	X								
Demographics	X								
Complete physical	X							X	
Body weight (kg)	X								
Height (cm) without shoes	X								
Brief physical		X							
Medical/medication/drug/alcohol history	X								
12-lead ECG	X 	X			X			X	2. Triplicate ECG at screening and CV risk factors
Vital signs 	X	X	X	X	X		X	X	3. Should be performed at the same time points as PK samples are taken
Urine drug/alcohol screen	X	X							
Pregnancy Test (women) 	X(S)		X(S/U)			X (S)	X(S)		4. Pregnancy test will be performed 3 times during screening, serum on day -28, day -7 to -4, and a serum or urine pregnancy test the day of the start of the study prior to dosing and a serum pregnancy test between day 10-12 (to coincide with a PK sample) and at the follow up visit.
HIV, Hep B and Hep C screen	X								
Clinical Laboratory Tests	X	X			X			X	

Day:	Screening	-1	1	2	3	4	Day 6 to 15	Follow-up (Day 17-19)	Notes
Allergen Challenge-SPT	X 		X 		X 	X 			5. SPT- Skin Prick Test measurements will be performed ~15-20mins post challenge 6. SPT using all 4 specified allergens 7. SPT will be performed at 6 hours post dose (see Section 6.4.1), and at 24 hours post last dose on day 3 8. SPT will be performed pre-dose on Day 1
TSH, free T4, T4, T3	X					X	X 	X	9. One sample between day 10-12 to coincide with PK sample
Cold Temp Test (Temp Test 4.0)	X		X 		X 	X 			10. Pre-dose 11. 6 hours post dose 12. 24 hours post last dose on Day 3
Randomisation		X							
Tolerability Assessment			←-----X  -----→						13. Tolerability assessment at pre – and ~6 hours post-dose
AE assessment			←-----X-----→				X		
Concomitant Medication		X	←-----X-----→				X		
Pharmacokinetic Blood Sample			X 	X 	X 	X 	X 	X	14. PK blood sample taken at pre dose, 1, 4, 8, 12hr post dose 15. One PK sample to be taken 24 hours post last dose on Day 3 16. One PK blood sample per day will be taken as follows: PK samples will be obtained on the following days (± 1 day): Day 6, 9, 12, & 15.

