### 6.1.4. Part C: Chronic Spontaneous Urticaria Cohort

Day:	Screening	1	2	3	4	5	6	7	8	Day 10 ( $\pm$ 1 day)	Day 15 ( $\pm$ 1 day)	Follow-up Day 22 ( $\pm$ 1 day)	Notes
Visit Window (relative to Day 1)	-28 to -7 												1. Screening can occur on any day between 28 days and 7 days prior to Day 1 dosing.
Informed Consent	X												
Demographics	X												
Complete physical	X											X	
Body weight (kg)	X												
Height (cm) without shoes	X												
Brief physical		X											
Medical/medication/drug/alcohol history	X												
12-lead ECG	X 	X						X				X	2. Triplicate ECG at screening and CV risk factors
Vital signs	X	X		X			X			X 	X 	X 	3. To be performed on same day as PK samples
Urine alcohol screen	X	X											
Pregnancy Test (Women of child bearing potential) 	X(S) 	X (U) 						X(U) 		X (S)	X(S)		4. A serum (S) pregnancy test will be performed on the day of screening. If the day of screening is between Days -13 and -7, a further pregnancy test will not be required until Day 1. However, if the day of screening is between Days -28 and -14, an additional serum pregnancy test will be required between Days -7 and -4.

Day:	Screening	1	2	3	4	5	6	7	8	Day 10 ( $\pm$ 1 day)	Day 15 ( $\pm$ 1 day)	Follow-up Day 22 ( $\pm$ 1 day)	Notes
													5. A urine pregnancy test is required prior to dosing on Day 1 & Day 7
HIV, Hep B and Hep C screen	X												
Clinical Laboratory Tests	X	X						X				X	
TSH, free T4, T4, T3	X							X		X6	X6	X6	6. Sample to be taken on same day as PK sample
Blood Sample for CD69 expression		X 		X 		X 			X 	X 	X 		7. Pre-dose 8. 4 hours post dose 9. Sample to be taken on same day as PK sample
Randomisation		X											
UAS-7 Diary	X 		X 	X					10. Screening UAS7 diary will be completed for the 7 successive days before Randomisation (Day 1). If there is a lapse in any day prior to Day 1 the subject must complete the full 7 days worth of diary entries again during the screening period. 11. The UAS-7 diary should be completed pre-dose on those days where dosing occurs				
QOL (DLQI)	X	X 							X				12. The baseline DLQI assessment on Day 1, looking back over the previous 7 days prior to dosing, should be completed pre-dose

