### Summary of Amendment Changes with Rationale

As a result of an informal preliminary data review from Part A of this study, several changes have been made to the design of Parts B and C of this study. The changes represent a more conservative strategy (staggering part C start relative to Part B), and reflect the necessity to fully understand the terminal elimination phase of GSK2646264 via the dermal route.

Because the terminal elimination phase was longer than anticipated it is proposed that thyroid function will be monitored via blood sample testing for the duration of exposure until the follow-up visit in parts B and C. The risk benefit with regards to thyroid function has not changed.

Changes are as follows:

[figure not shown]
- Part B and C have changed from a bilateral to a placebo-controlled randomised parallel design 3:1 active to placebo.
- An informal review of data from the first 4 patients of Part B will be performed before starting part C.
- The number of subjects in Part C has increased (from n=12 up to n=16); and a 2-week PK/PD sampling period for parts B & C has been implemented.
- Free T4, T4 and T3 monitoring has been included for parts B and C at intervals until the follow-up visit.

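### In Parts B and C, after the first dosing day, haematology and liver chemistry are scheduled only on the last dosing day and 14 to 16 days later, which does not match Table 6 or let the ALT rule act reliably before a dose

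*Protocol*

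**What the plan says.** - **Risk strategy.** Protocol Table 6, row on immune cell effects, cites neutropenia rates of 5.9% and 6.6% with an oral SYK inhibitor against 0.7% on placebo. The mitigation reads "Subjects will undergo regular haematological assessments, including white blood cell counts during the study" and "Treatment would be stopped if laboratory test results are identified that would put the safety of the subject at risk". No frequency and no neutrophil threshold are given.
- **Liver rule.** Under Section 5.7.1 study treatment stops for a subject "if the following liver chemistry stopping criteria is met"; the criterion is ALT at or above 3 times ULN.
- **Part B schedule (6.1.3).** The row "Clinical Laboratory Tests" is marked at Screening, Day -1, Day 3 and follow-up on Day 17–19. Doses are on Days 1, 2 and 3.
- **Part C schedule (6.1.4).** The same row is marked at Screening, Day 1, Day 7 and follow-up on Day 22 (±1). Section 3.1.5 puts the doses on Days 1, 4 and 7.
- **Timing.** Neither table says whether the Day 3 or Day 7 sample is taken before the dose, or when the result is due.
- **Part A group 2 (6.1.2, note 9).** Liver tests were drawn pre-dose on Days 2 and 4, with "results to be communicated to the GSK Medical monitor on the same day".
- **Elimination.** Section 3.2.2.3 reports that modelling of Part A and the first four Part B subjects "lead to an estimation of the half life of 57 hours". Appendix 8 explains that, once slow elimination was known, Amendment 3 provided that in Parts B and C "thyroid function will be monitored via blood sample testing for the duration of exposure until the follow-up visit".

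**The concern.** Table 6 and Section 5.7.1 depend on laboratory results being available while there is still a dose to withhold. With three doses and one on-treatment sample on the day of the last of them, that is largely left to chance. The dose-limiting toxicity definition in Section 5.5.1 is affected too: a severe laboratory abnormality counts only within 6 h of a dose in Part B or 24 h in Part C. No panel is scheduled in that window after Part B doses 1 and 2 or after the Part C Day 4 dose.

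The second gap follows the last dose. Slow elimination prompted longer thyroid and PK sampling, but haematology and liver chemistry were not extended. A neutrophil fall or ALT rise that came and went within two weeks could be missed. Clinical laboratory tests are part of the primary endpoint (Section 2.1), so a clean result in patients would partly reflect when blood was drawn. There is also a loss of information: Appendix 1 allows a liver-event PK sample only within 24 h of the last dose, so an ALT rise first found at follow-up cannot have one.

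**Working it through.** **1. Schedules side by side** (Protocol 3.1.4, 3.1.5, 6.1.3, 6.1.4; the SAP's schedule tables rest on Amendment 2 and are not used)

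| | Doses | Haematology and chemistry | Later blood draws without them |
|---|---|---|---|
| Part B | Days 1, 2, 3 | Screening, Day -1, Day 3, Day 17–19 | Day 2, Day 4, Days 6, 9, 12, 15 (±1) |
| Part C | Days 1, 4, 7 | Screening, Day 1, Day 7, Day 22 (±1) | Day 4, Day 10, Day 15 (last two ±1) |

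Gap after the last-dosing-day draw: Part B 17 − 3 = 14 to 19 − 3 = 16 days; Part C 21 − 7 = 14 to 23 − 7 = 16 days.

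**2. What each draw can act on**

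- Before dose 2: Part B has only pre-treatment samples. Part C has the Day 1 sample, also without stated timing. Even if taken after application, it would be within hours of the first dose.
- Before dose 3: no further panel, unless the Day 3 or Day 7 sample is drawn and resulted before application. The protocol allows this but does not require it.
- After dose 3: nothing until follow-up.

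**3. The plan's own figure.** The 57 h half-life cannot be reproduced, because the model data are not given. It is consistent with the 12-day contraception period in Sections 4.2.1.3 and 4.2.1.4: 5 × 57 / 24 = 11.9 days.

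**4. Share of exposure after the last-dosing-day draw.** Assumptions not in the documents: one compartment, three equal doses, immediate input. For a draw h hours after the last dose, the share of total AUC still to come is the average over doses of 2^(−hours since that dose / 57).

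- Part B, h = 0: (1 + 2^(−24/57) + 2^(−48/57)) / 3 = (1 + 0.747 + 0.558) / 3 = 0.77
- Part C, h = 0: (1 + 2^(−72/57) + 2^(−144/57)) / 3 = (1 + 0.417 + 0.174) / 3 = 0.53
- At h = 12 both are multiplied by 2^(−12/57) = 0.864: Part B 0.66, Part C 0.46

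The Part C share drops below one half about 5 h after the Day 7 dose.

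**5. Drug left at follow-up.** As a fraction of the level just after the last dose: 2^(−336/57) = 0.017 to 2^(−384/57) = 0.009, so about 1–2%. At the Part C Day 10 and Day 15 draws, which carry no count or ALT, it is 2^(−72/57) = 0.42 and 2^(−192/57) = 0.10.

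**6. Sensitivity** (draw 0–12 h after the last dose)

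| Assumption | Part B | Part C |
|---|---|---|
| 57 h, immediate input | 66–77% | 46–53% |
| 57 h, 8 h absorption half-life | 75–83% | 51–56% |
| 36 h, immediate input | 54–68% | 35–44% |
| 72 h, immediate input | 72–81% | 52–58% |

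**The case against.** The case for leaving the schedule alone has substance.

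- **Systemic exposure is low.** The neutropenia rates belong to a different compound given orally. The geometric mean Cmax after four days in Part A was 5.59 ng/mL (Section 3.2.2.2) against a CD69 IC20 of 1150 ng/mL (Section 3.2.2.1), and 1150 / 5.59 is about 206-fold. CD69 itself is sampled during the gap. This stands, and it lowers the urgency.
- **Earlier data were reviewed.** Group 2 of Part A had full panels on Days 5, 7 and 8. Part A and the first four Part B subjects were reviewed before progression, without clinically significant safety issues. Dosing was then reduced to 3.5% BSA for the rest of Part B and to every third day in Part C. This also stands.
- **The Part A precedent is partial.** Group 1 had no panel on any dosing day, and note 9 in group 2 covers liver tests only. It is a model for timing and reporting, not for on-treatment neutrophil counts.
- **Thyroid is different.** Thyroid sampling followed an animal finding with this compound, so extending it alone can be explained.
- **Tests can be added.** Sections 6 and 6.3 allow extra safety time points without an amendment. That makes the change easy, but a discretionary power does not supply the samples.

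A reader might infer that no laboratory result could prevent any dose. The documents do not go that far: a Part C Day 1 abnormality could stop Days 4 and 7, and a Day 3 or Day 7 sample could be resulted in time. A reader might also infer a specific neutropenia stopping rule, but Table 6 has only a general laboratory provision.

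**Conclusion.** The point holds as a mismatch between the stated risk strategy and the schedules. After the first dosing day, haematology and liver chemistry are taken once on the last dosing day, at an unstated time, and once 14 to 16 days later. That does not amount to regular counts, and it does not allow the laboratory stopping provisions to be relied on before a dose.

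About 66–77% of exposure in Part B and about half (46–53%) in Part C falls after the last-dosing-day draw, and 1–2% of the drug remains at follow-up. These figures rest on the 57 h half-life and on the assumed one-compartment model with equal doses and immediate input. It would be tempting to say that over half of the exposure goes unmonitored in both parts. That is firm only for Part B; in Part C it depends on draw time, absorption and half-life. Unmonitored would also be too strong: a lasting abnormality would be found at follow-up, and the risk is of missing one that resolves in between.

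Given the low observed systemic exposure, this should be corrected but is not a critical flaw.

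**What to change.** Reconcile Table 6 and Section 5.7.1 with Sections 6.1.3 and 6.1.4. Specifically:

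- **Part C:** run the haematology and liver chemistry tests already defined in Section 6.3.4 on the blood draws of Days 4, 10 and 15.
- **Part B:** run them on the Day 2 pre-dose draw and on some of the Day 6–15 PK draws. Including the Day 6 draw matters most. With a pre-dose Day 3 sample, it cuts the largest share of exposure between consecutive panels from 0.768 × (1 − 2^(−360/57)) = 76% (Day 3 to Day 18) to 0.768 × (1 − 2^(−72/57)) = 45%. In Part C the Day 10 draw cuts it from 0.530 × (1 − 2^(−360/57)) = 52% (Day 7 to Day 22) to 0.530 × (1 − 2^(−72/57)) = 31%.
- **Dosing-day samples:** state their timing relative to the dose and how quickly results are reported, as note 9 does for Part A group 2.

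Doses, thresholds and stopping actions stay as written. The SAP's schedule and laboratory displays need the added time points.

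The cost is a few mL more blood per subject and some extra local laboratory tests, with no new visit, staff or procedure. The added volume must be checked against the 500 mL limit in Section 6, since sample volumes are in the Study Procedures Manual.

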## 4. STUDY POPULATION

### 4.1. Number of Subjects

The aim is to achieve approximately 18 randomised evaluable subjects in Part A (9 subjects in dosing group 1 and 9 subjects in dosing group 2), approximately 12 randomised evaluable subjects who complete the study in Part B and approximately 16 subjects in Part C. In Parts A and B, it is anticipated that a proportion of subjects will not demonstrate weal and flare at the screening skin prick test (See Section 4.2.1.2 and Section 4.2.1.3). However these proportions are not known, so enough subjects will be enrolled to achieve the target study population.

### 4.2. Eligibility Criteria

Protocol waivers or exemptions are not allowed with the exception of immediate safety concerns. Therefore, adherence to the study design requirements, including all those specified in the Time and Events Table, are essential and required for study conduct.

Specific information regarding warnings, precautions, contraindications, adverse events, and other pertinent information on the GSK investigational product or other study treatment that may impact subject eligibility is provided in the IB.

Deviations from inclusion and exclusion criteria are not allowed because they can potentially jeopardize the scientific integrity of the study, regulatory acceptability or subject safety. Therefore, adherence to the criteria as specified in the protocol is essential.

For a subject to be included in the study they must fulfil all requirements for both the 'All subjects' Inclusion and Exclusion Criteria and then specific inclusion and exclusion for either healthy subjects, Cold urticaria subjects or Chronic Spontaneous subjects as shown in Section 4.2.

For those criteria where an investigator's decision will be required to it will be documented on every occasion.

